7 response is limited to a small subset of patients. Combination treatment with peginterferon and
8 NUCs has been attempted in several randomized controlled trials, with no apparent advantage over
9 either agent given alone. In these studies however, treatment with peginterferon was initiated either
10 simultaneously or shortly after NUCs administration. The efficacy of peginterferon following long-
11 term viral suppression with NUCs was only tested in one small pilot study, nevertheless showing
12 60% HBsAg loss rate.

13 The underlying mechanisms responsible for improved efficacy of peginterferon in this setting are
14 unknown and warrant further investigation. In this single arm study we propose to evaluate the
15 efficacy and mechanisms associated with response to peginterferon add-on therapy following a
16 minimum of 192 weeks of viral suppression induced by NUCs in a group of chronic HBV infected
17 patients. Sixty patients with either HBeAg positive (n=30) or negative (n=30) chronic HBV infection
18 will be enrolled to this study. After medical evaluation and pretreatment liver biopsy, treatment with
19 subcutaneous injections of pegylated interferon alpha-2a 180 µg per week will be given for a total of
20 24 weeks, followed by an off-treatment evaluation period of 48 weeks. A second liver biopsy will be
21 performed six hours following the first peginterferon injection. Primary end-point for this study will
22 be the change in interferon-stimulated-genes response before and after first interferon injection in
23 responders versus non-responders to treatment. The responsiveness to IFN-based therapy of
24 treatment responders vs nonresponders will additionally be evaluated by studying intrahepatic and
25 peripheral blood natural killer cells. The study will also assess HBeAg and HBsAg loss and
26 seroconversion rates in comparison to historical controls treated with either peginterferon or NUCs
27 monotherapy. Finally, we will assess whether treatment responders develop an HBV-specific T cell
28 response similar in quantity and quality to that of patients who spontaneously resolve HBV infection.

29
30

Table of Contents

1		
2	Précis	3
3	BACKGROUND	5
4	HYPOTHESIS	8
5	SPECIFIC AIMS	8
6	PROTOCOL OVERVIEW	8
7	INCLUSION/EXCLUSION CRITERIA	9
8	Inclusion criteria: HBeAg positive group	9
9	Inclusion criteria: HBeAg negative group	9
10	Exclusion criteria (for both eAg positive and negative patients)	10
11	STUDY DESIGN AND PROCEDURES	11
12	Screening	11

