3. To identify pre- and on-treatment predictors of serological response to peginterferon add-on/nucleos(t)ide combination therapy.
4. To determine if there are differences in epigenetic regulation of cccDNA between HBeAg positive and negative CHB at baseline and following a single dose of peginterferon treatment

PROTOCOL OVERVIEW

We intend to enroll a total of 60 patients with HBeAg positive (n=30) and HBeAg negative (n=30) chronic HBV infection, who have been on-treatment with one or more nucleos(t)ide analogues for at least 192 weeks prior to study enrollment with maintained viral suppression (HBV DNA level <100 IU/ml). After a thorough medical evaluation and liver biopsy, participants will receive therapy with subcutaneous injections of peginterferon-alpha 2a at a dose of 180mcg per week for a total of 24 weeks. A second liver biopsy will be performed 6 hours following the first peginterferon injection for the purpose of assessing ISGs, intrahepatic NK cell quantity and function and intrahepatic viral biomarker response patterns. Most interferon induced genes achieve maximal response in the liver and periphery within 4 hours, begin to decline by 8 hours, and return to baseline levels by 24 hours post-administration of interferon. Because peginterferon is slower to be absorbed we have selected the six hour rather than a four hour time point.[38]

1 Patients will be followed carefully on weeks 0, 2, 4, 8, 12 and 24 during treatment and at 12 week
2 intervals thereafter until 48 weeks post-treatment.
3 During study visits patients will be assessed for compliance with study medications, as well as the
4 development of any treatment related side effects and/or adverse reactions. In addition, blood will
5 be drawn periodically for the assessment of routine blood tests, quantitative viral biomarker levels,
6 serological response markers and immune cell functional status.
7

8 **INCLUSION/EXCLUSION CRITERIA** 9

10 **Inclusion criteria: HBeAg positive group**

- 11
- 12 1) Age >18 years and older, male or female.
- 13 2) Known serum HBsAg and HBeAg positivity at the time of screening.
- 14 3) Ongoing treatment with one or more NUCs for at least 192 weeks before study entry.
15 Subjects may have a brief interruption of treatment for medical reasons (e.g. breast feeding)
16 not to exceed 8 weeks and none within the 48 weeks before study entry.
- 17 4) HBV DNA levels <100 IU/mL, measured at least 12 months prior to, and upon enrollment to
18 the study.

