- 22 10) Hepatocellular carcinoma (HCC), or the presence of a mass on imaging studies of the liver
- 23 that is suggestive of HCC, or an alpha-fetoprotein level of greater than 500 ng/mL.
- 24 11) eGFR < 50 ml/min, serum creatinine > 1.3 mg/dl or urine protein >1 gram/24-hours
- 25 12) History of hypersensitivity to pegylated interferon-alpha
- 26 13) Platelet count <70 mm³/dL
- 27 14) Hgb <12 g/dL for males and <11 g/dL for females
- 28 15) Active ethanol/drug abuse/psychiatric problems such as major depression, schizophrenia,
- 29 bipolar illness, obsessive-compulsive disorder, severe anxiety, or personality disorder that,
- 30 in the investigator's opinion, might interfere with participation in the study.
- 31 16) History of malignancy or treatment for a malignancy within the past 3 years (except
- 32 adequately treated carcinoma in situ or basal cell carcinoma of the skin).
- 33 17) Any medical condition requiring, or likely to require, chronic systemic administration of
- 34 corticosteroids or other immunosuppressive medications during the course of this study.
- 35 18) History of immune-mediated disease, or cerebrovascular, chronic pulmonary or cardiac
- 36 disease associated with functional limitation, retinopathy, uncontrolled thyroid disease,

- 1 poorly controlled diabetes or uncontrolled seizure disorder, as determined by a study
 2 physician.
- 3 19) Presence of conditions that, in the opinion of the investigators, would not allow the patient
 4 to be followed in the current study for at 1 year.
- 5 20) For subjects who interrupt therapy, documentation of a viral load >1,000 IU/ml while off
 6 therapy.
 7

8 **STUDY DESIGN AND PROCEDURES**

9

10 **Screening**

11 Eligible patients will be seen in the outpatient liver clinic of the NIH Clinical Center. At the screening
 12 visit, potential benefits and risks associated with the study will be explained to the study participants
 13 by an investigator in laymen's language. Written informed consent will be obtained and documented
 14 in the participant's chart. Whenever possible, the informed consent form will be provided to the
 15 potential participants in advance. Only the principal and associate investigators from the Liver
 16 Disease Branch, NIDDK, will be eligible to obtain consent for this study.
 17

18 The following screening procedures will be performed:

- 19 (1) Obtain signed informed consent
- 20 (2) History and physical examination
- 21 (3) Symptom questionnaire

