- 22 (4) Fatigue questionnaire (Promise 7)
- 23 (5) Visual analogue scale
- 24 (6) Routine blood panel: Chemistry 20 (sodium, chloride, potassium, bicarbonate, calcium,
 25 phosphate, magnesium, glucose, blood urine nitrogen, creatinine, uric acid, ALT, AST,
 26 LDH, CPK, Alkaline Phosphatase, total and direct bilirubin, albumin, total protein), CBC
 27 (hematocrit, hemoglobin, white blood cell count and differential, platelet count).
 28 Testing will also be done for anti-HAV, HBsAg, anti-HBs, HBeAg, anti-HBe, anti-HBc,
 29 anti-HCV, and stored sample for IL-28b testing. Baseline HBV DNA level by quantitative
 30 PCR (COBAS Ampliprep/COBAS Taqman HBV v2.0 Test: Roche Diagnostics, lower limit
 31 of quantification 116 copies /ml or 20 IU/ml, lower limit of detection 6 IU/ml)
- 32 (7) Extended blood panel: alpha fetoprotein, gGT, immunoglobulins, rheumatoid factor,
 33 ANUCs, SMA, lipid panel, thyroid panel, INR, reticulocyte count, ESR.
 34

- 1 (8) Research blood- one 10 ml serum and one 10 ml plasma tube stored frozen in 0.5-1.0
2 mL aliquots). The stored serum and plasma will be used to measure selected cytokines,
3 interferon-stimulated gene products [including IP10], quantitative HBsAg level (by
4 using the Roche Elecsys HBsAg automated quant assay) and for future research.
- 5 (9) Fifty milliliters of whole blood (green top tubes) for baseline immunological studies: NK
6 cell responses, CD4+ and CD8+ T cell HBV specific responses (peripheral blood
7 mononuclear cell [PBMC] studies)
- 8 (10) Urine tests: routine urinalysis and a pregnancy test for females of childbearing
9 potential
- 10 (11) Transient elastography
- 11

12 **Admission for pretreatment liver biopsy**

13

14 Once patients are deemed eligible to participate in the study based on results of the screening
15 labs, they will have 12 weeks to complete the liver biopsy and to begin add-on therapy with
16 peginterferon. Eligible patients will be admitted to 5NW to undergo a percutaneous liver biopsy.
17 The initial liver biopsy will be mostly for research purposes to measuring baseline levels of ISG
18 expression, pregenomic and cccDNA concentration and frequency and activity of liver infiltrating
19 HBV-specific NK cells but will also be used for the purpose of grading and staging of liver disease
20 before treatment and will provide useful information to the clinician and patient on whether the
21 liver disease is improving on current therapy. Grading and staging of the liver biopsy will

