32

33 **End of Add-on Peginterferon Treatment (Week 24 \pm 3 days)**

34 At week 24, all subjects will discontinue peginterferon alfa-2a add-on therapy (but continue the
 35 NUCs and undergo the following evaluation:

- 1 1) Physical examination
- 2 2) Symptom questionnaire
- 3 3) Fatigue questionnaire (Promise 7)
- 4 4) Visual analogue scale
- 5 5) Assessment of adverse events, concomitant medications and adherence
- 6 6) Blood will be drawn for Chemistry 20 (sodium, chloride, potassium, bicarbonate, calcium,
- 7 phosphate, magnesium, glucose, blood urine nitrogen, creatinine, uric acid, ALT, AST, LDH,
- 8 CPK, Alkaline Phosphatase, total and direct bilirubin, albumin, total protein), CBC
- 9 (hematocrit, hemoglobin, white blood cell count and differential, platelet count).
- 10 7) 50 mL of blood in heparinized green top tubes for NK and T cell analysis.
- 11 8) Urine tests: routine urinalysis and creatinine, phosphate and beta-2-microglobulin
- 12 9) HBV DNA viral load, HBeAg, anti-HBe, HBsAg, anti-HBs and quantitative HBe and HBs
- 13 measurement
- 14 10) Blood sample for storage (10 mL of blood separated into serum and plasma stored frozen in
- 15 0.5-1.0 mL aliquots)
- 16 11) Females of child bearing potential: Pregnancy test
- 17 12) TSH

18

19 **Post-treatment weeks 12, 24, 36 (\pm 5 days)**

- 20 1) Limited clinical evaluation
- 21 2) Symptom questionnaire
- 22 3) Visual analogue scale
- 23 4) Routine blood panel: Chemistry 20 (sodium, chloride, potassium, bicarbonate, calcium,
- 24 phosphate, magnesium, glucose, blood urine nitrogen, creatinine, uric acid, ALT, AST, LDH,
- 25 CPK, Alkaline Phosphatase, total and direct bilirubin, albumin, total protein), CBC
- 26 (hematocrit, hemoglobin, white blood cell count and differential, platelet count).
- 27 5) HBV DNA viral load, HBeAg, anti HBe, HBsAg and anti HBs levels
- 28 6) Blood sample for storage (10 mL of serum and 10 ml of plasma stored frozen in 0.5-1.0 mL
- 29 aliquots)
- 30 7) 50 mL of blood in heparinized green top tubes for NK and T cell analysis.

31

32

33 **Final study visit week 48 post-treatment (\pm 5 days)**

- 34 1) Limited clinical evaluation
- 35 2) Symptom questionnaire

- 1 3) Fatigue questionnaire (Promise 7)
 2 4) Visual analogue scale
 3 5) Routine blood panel: Chemistry 20 (sodium, chloride, potassium, bicarbonate, calcium,
 4 phosphate, magnesium, glucose, blood urine nitrogen, creatinine, uric acid, ALT, AST, LDH,

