 5 CPK, Alkaline Phosphatase, total and direct bilirubin, albumin, total protein), CBC
 6 (hematocrit, hemoglobin, white blood cell count and differential, platelet count).
 7 6) Extended blood panel: alpha fetoprotein, gGT, immunoglobulins, rheumatoid factor, ANA,
 8 SMA, lipid panel, INR, reticulocyte count, ESR.
 9 7) 50 mL of blood in heparinized green top tubes for NK and T cell analysis.
 10 8) HBV DNA viral load, HBeAg, anti HBe, HBsAg, and anti HBs levels and quantitative HBe and
 11 HBs measurement
 12 9) Blood sample for storage (10 mL of serum and 10 ml of plasma stored frozen in 0.5-1.0 mL
 13 aliquots)
 14 10) Fibroscan
 15

16 **Table 1: List of study related procedures**
 17

Procedure	Screen	Pre-Rx biopsy	Day 0	Wk 2, 4, 8	Wk 12	Week 24 End of Rx	Post-Rx wk 12, 24, 36	Post-Rx wk 48, End of Study
H&P/breif clinical evaluation, compliance, AE, concomit. drugs, etc	X	X	X	X	X	X	X	X
Symptom questionnaire	X	X	X	X	X	X	X	X
Visual Analog Scale	X	X	X	X	X	X	X	X
Promis 7	X	X	X	wk 2		X		X
Chem 20	X	X	X	X	X	X	X	X
CBC	X	X	X	X	X	X	X	X
Anti-HAV	X							
HBsAg	X	X	X	X	X	X	X	X
HBsAg quantitative			X		X	X		X
anti-HBs	X							
HBeAg	X	X	X	X	X	X	X	X
HBeAg quantitative			X		X	X		X
anti-HBe	X							
anti-HBc	X							

anti-HCV	X							
IL28B	X							
HBV DNA	X	X	X	X	X	X	X	X
AFP	X							X
gGT	X							X
Immunoglobulins	X							X
rheumatoid factor	X							X
ANA	X							X
SMA	X							X
Lipid panel	X							X
thyroid panel	X				TSH	TSH		
INR	X							X
reticulocyte	X							X
ESR	X							X
storage - 5mL serum and 5mL plasma	S&P	Serum	Serum	S&P	S&P	S&P	S&P	S&P
Immunology - 50mL	X	X	X	X	X	X		X
Urine pregnancy	X		X	X	X	X		
UA	X					X		
Urine creatinine, phosphate, beta-2-microglobulin						X		
Liver Biopsy		X	Time d					
Abdominal u/s		X						
CXR		X						
EKG		X						
Fibroscan	X							X

1

2

3

4

5

ASSESSMENT OF RESPONSE

6

Clinical Definitions

7

8

a) **Loss of HBeAg (HBeAg-positive patients only):** loss of detectable HBeAg with or without anti-HBe seroconversion confirmed on 2 consecutive visits at least 12 weeks apart.

9

10

b) **Loss of HBsAg:** Loss of HBsAg, with or without anti HBs seroconversion confirmed on 2 consecutive visits at least 12 weeks apart.

11

- 1 c) **Sustained response:** virological, serological, biochemical, or combined response present at
2 the time of last observation and at least six months after stopping therapy.

3

4

5 The primary goals of this study are centered on understanding the mechanisms, and identification of

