6 predictive factors associated with a favorable response to peginterferon therapy when added on to
7 long-term NUCs treatment, in patients with HBeAg positive and negative chronic HBV infection.

8

9 **Primary end-points**

10

- 11 1) The primary end-point for this study will be the change in level of ISG expression and NK cell
12 responses before and after 1st peginterferon injection in responders versus non-responders
13 to peginterferon add-on therapy.
- 14 2) Proportion of eAg positive patients showing eAg loss with or without seroconversion at end
15 of treatment and 24 and 48 weeks off therapy.
- 16 3) Proportion of eAg positive patients showing sAg loss with or without seroconversion at end
17 of treatment and 24 and 48 weeks off therapy
- 18 4) Proportion of eAg negative patients showing sAg loss with or without seroconversion at at
19 end of treatment and 24 and 48 weeks off therapy

20

21 **Secondary endpoints**

22

- 23 1. Level of qHBsAg decline at treatment week 12, at end of treatment and 24 and 48 weeks off
24 therapy, compared to pretreatment levels in eAg positive and negative patients
- 25 2. Level of qHBeAg decline at treatment week 12, at end of treatment and 24 and 48 weeks off
26 therapy, compared to pretreatment levels in eAg positive and negative patients
- 27 3. Correlation of qHBsAg levels at initial evaluation, week 12,24,36 and 48 with intrahepatic
28 pregenomic and cccDNA concentration before and after initiation of peginterferon in
29 responders versus non-responders to treatment.
- 30 4. Intrahepatic pregenomic and cccDNA concentration before and after starting treatment with
31 peginterferon.
- 32 5. Epigenetic alterations in HBeAg positive and negative patients following first 1st
33 peginterferon injection compared to pretreatment levels as measured by chromatin
34 immunoprecipitation (ChIp) assays

- 1 6. Frequency and functional activity of circulating and liver infiltrating, HBV-specific T-cells,
2 measured before and during treatment in responders versus non-responders to
3 peginterferon add-on therapy.
4

5 DOSE CHANGES 6

7 **Stopping peginterferon therapy:** 8

9 Add-on peginterferon will be discontinued early for any of the following reasons:

- 10 a) **Toxicity**- the dose of peginterferon will be modified or discontinued according to Table 1:
11 Peg-Interferon Alfa-2a Dose Modification Guidelines (see below).
12 b) **Withdrawal of informed consent** (subject's decision to withdraw for any reason.

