It is not possible to calculate power for the primary endpoints. We have calculated power for the secondary endpoints of the rates of HBeAg and HBsAg loss. Response rates in patients in both groups will be compared to historical controls of HBeAg positive and negative. It is assumed that if these patients were followed for an additional year without peginterferon, only 10% of the HBeAg positive patients would become HBeAg negative and 5% of the HBeAg negative patients would become HBsAg negative. A sample size of 29 HBeAg positive and 27 HBeAg negative patients will provide the study with a statistical power of 80% to detect a difference of 25% (35% versus 10% for HBeAg loss and 30% versus 5% for HBsAg loss). The sample size was increased to 30 patients in each arm to allow for withdrawals.

Variables to be analyzed in association with a serological response will include: baseline ALT and HBV DNA level, liver histology, HBV genotype, IL28B genotype, duration of NUC therapy, and ISG levels. Patients with missing data or who drop out of the study will be considered as treatment failures on an intention to treat basis. For comparison of means, Student's t-test will be used. All reported p-values will be 2-sided.

Demographics and Baseline Characteristics

The following will be summarized for treated subjects:

- Demographics: age, race, gender, geographic region, ethnicity;
- Disease characteristics at baseline: HBV DNA level, HBV genotype, IL28B SNP genotype and cirrhosis status, duration of NUC therapy;
- Physical measurements at baseline; height, weight, body mass index, hip and waist circumference;
- Laboratory tests at baseline;

Analysis plan

To address the primary hypothesis that ISG levels are related to virological response to peginterferon, the ISG analysis of the on treatment liver biopsy at 6 hours after the first dose of interferon will be correlated with off-peginterferon serological outcome (HBeAg loss/seroconversion and HBsAg loss). To address the hypothesis that ISG levels are related to HBsAg levels, the ISG analysis of the on treatment liver biopsy will be correlated with HBsAg levels at weeks 4, 12, 24.. The

1 analyses will be stratified by HBV genotype and duration of NUC therapy.

2

3 **Analysis methodology**

4

5 The analysis will be based on standard approaches to analysis of microarray data. Since the software
6 and approaches change frequently in this field, we will provide a broad outline of the approach

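### Exclusion criterion 19 screens for one year of follow-up, but the last reading of primary end-points 2–4 falls 72 weeks after the first peginterferon dose

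*Combined protocol and SAP*

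**What the plan says.** Exclusion criterion 19 excludes patients with conditions that, in the investigators' opinion, would not allow them "to be followed in the current study for at 1 year". A word such as *least* seems to be missing after *at*, and the criterion does not say when the year starts.

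The other relevant statements are:

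- **Length of study.** The Précis gives treatment of "24 weeks, followed by an off-treatment evaluation period of 48 weeks". The Protocol Overview schedules visits at 12-week "intervals thereafter until 48 weeks post-treatment", and the Monitoring section ends with the "Final study visit week 48 post-treatment".
- **Time to first dose.** Under Admission for pretreatment liver biopsy, once patients are found eligible on their screening "labs, they will have 12 weeks to complete the liver biopsy and to begin add-on therapy with" peginterferon.
- **Reading times.** Primary end-points 2–4 (HBeAg or HBsAg loss) are read at end "of treatment and 24 and 48 weeks off therapy".
- **Confirmation.** Under Clinical Definitions, antigen loss must be "confirmed on 2 consecutive visits at least 12 weeks apart".
- **Missing outcomes.** Under Power calculation, "Patients with missing data or who drop out of the study will be considered as treatment failures".

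No other eligibility criterion asks for availability to the final visit.

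**The concern.** The availability that the criterion asks for is shorter than the study. A candidate known at entry to be available for a little over a year passes it, yet cannot attend the last scheduled reading of three of the four numbered primary end-points. Because missing outcomes count as failures, that patient would be recorded as a failure at week 72 whatever the true outcome. The same holds for antigen loss first seen 24 weeks off therapy: its confirming visit falls after the year has ended.

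At stake is a downward shift in the recorded response rate at the last primary reading, from losses that could have been foreseen at screening. The HBeAg-positive group has little slack: its calculated size of 29 was raised by only one patient to allow for withdrawals.

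**Working it through.** **Timeline, in weeks from first peginterferon dose**

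| Event | Week |
|---|---|
| End of treatment | 24 |
| 12 weeks off therapy | 36 |
| 24 weeks off therapy | 24 + 24 = 48 |
| 36 weeks off therapy | 24 + 36 = 60 |
| 48 weeks off therapy, final visit | 24 + 48 = 72 |

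One year is about 52 weeks.

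- *Year counted from first dose:* weeks 24, 36 and 48 are covered; weeks 60 and 72 are not. The shortfall is 72 − 52 = 20 weeks. Loss first seen at week 36 can be confirmed at week 48. Loss first seen at week 48 needs week 60, which is outside the year.
- *Year counted from eligibility, full 12-week window used:* the last reading is at 12 + 72 = 84 weeks, a shortfall of 84 − 52 = 32 weeks. The year ends at 52 − 12 = week 40 from first dose, so the 24-weeks-off reading is missed as well.

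**The plan's own sample sizes**

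The Power calculation gives 29 patients (35% versus 10%, HBeAg loss) and 27 (30% versus 5%, HBsAg loss) for 80% power. Alpha is not stated; I assume 0.05 two-sided. The one-sample formula with the variance at the alternative rate is

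n = (z₀.₉₇₅ + z₀.₈₀)² × p₁(1 − p₁) / (p₁ − p₀)², with (1.960 + 0.842)² = 7.849.

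- HBeAg: 7.849 × 0.35 × 0.65 / 0.25² = 28.57, rounded up to 29.
- HBsAg: 7.849 × 0.30 × 0.70 / 0.25² = 26.37, rounded up to 27.

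Both match, which supports the assumed alpha.

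**Illustration of the effect at week 72**

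Assume that k of 30 patients in a group are unavailable at week 72, that this is unrelated to outcome, and that they are scored as failures. The recorded rate becomes p₁ × (1 − k/30). The exact one-sample binomial test with n = 30 and an upper tail of at most 0.025 succeeds at:

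- HBeAg: 8 or more of 30 (upper tail 0.0078 at a true rate of 10%; 7 or more gives 0.0258, just too large).
- HBsAg: 5 or more of 30 (upper tail 0.0156 at a true rate of 5%).

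| k lost | HBeAg rate | HBeAg exact power | HBsAg rate | HBsAg exact power |
|---|---|---|---|---|
| 0 | 35.0% | 87.6% | 30.0% | 97.0% |
| 1 | 33.8% | 84.7% | 29.0% | 96.1% |
| 2 | 32.7% | 81.3% | 28.0% | 95.0% |
| 3 | 31.5% | 77.5% | 27.0% | 93.7% |

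The approximate formula that reproduces 29 and 27 starts lower. At n = 30 it gives 81.9%, 78.8%, 75.4% and 71.7% for HBeAg, and 84.8%, 82.6%, 80.1% and 77.5% for HBsAg. I rely on the exact figures; the direction is the same in both.

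**The case against.** The strongest reply is that criterion 19 does not set the length of follow-up. It is an investigator's judgement about foreseeable obstacles. Follow-up is set by the visit schedule, which takes every patient to 48 weeks post-treatment, and nothing releases anyone at one year. Participants have been on NUCs for at least 192 weeks, and about 85% are expected from the branch's own clinic, so few may be planning to leave. Eligibility is reviewed again at biopsy admission and at Day 0, so the screen can be applied at first dose, where the shortfall is 20 weeks and not 32. Two of the three reading times fit within one year of first dose.

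All of this stands, and it limits the point. It does not remove the mismatch: even read as at least 1 year, the threshold lies below the 72 weeks that the end-points need.

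Two stronger readings are tempting, and the documents support neither.

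- **A reader might infer that the criterion builds missing outcomes into the trial and so costs it power.** The criterion permits such losses but does not cause them, and the documents give no count of affected patients. The Power calculation also names no time point, and its comparator is an additional year without peginterferon. If the test is at 24 weeks off therapy, a patient who leaves one year after first dose is not missing.
- **A reader might infer that responders will be mislabelled in the ISG and NK-cell comparison.** The Analysis plan uses serological outcome off peginterferon without naming week 72. A patient with confirmed loss by 24 weeks off therapy has an observed outcome. Mislabelling through this route is possible only if responder status is taken at week 72.

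Failure scoring is also conservative for the comparison with historical rates.

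**Conclusion.** The point holds as an inconsistency between an eligibility threshold and the trial's own end-points. It is minor and cheap to correct. One year falls about 20 weeks short of the last primary reading counted from first dose, and up to 32 weeks short counted from eligibility. What is exposed is the 48-weeks-off reading and the confirmation of antigen loss first seen at week 48. The 24-weeks-off reading is exposed only if the year runs from eligibility.

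Any loss of power is hypothetical. It depends on an assumed 1 to 3 losses in 30, on a test at week 72 and on two-sided alpha of 0.05. Under those assumptions the exact power for HBeAg loss drops below 80% only at three losses, and the exact power for HBsAg loss stays well above it throughout.

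**What to change.** In exclusion criterion 19, replace the one-year wording with follow-up *through the final study visit, 48 weeks post-treatment (72 weeks from the first peginterferon dose)*. State that this is assessed at screening and again in the Day 0 eligibility review. That supplies the missing start point and makes the 12-week window immaterial.

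Sample size, visits and treatment do not change. The cost is one line of text and the exclusion of a few candidates with foreseeable obstacles to full follow-up.
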